5. LIST OF ABBREVIATIONS

Abbreviation	Term
AE	Adverse Event/Adverse Experience
CFR	Code of Federal Regulations
CRA	Clinical Research Associate
CRF	Case Report Form
CRO	Contract Research Organization
DMP	Data Management Plan
EDC	Electronic Data Capture
EMG-NCV	Electromyopathy and Nerve Conduction Velocity
FDA	Food and Drug Administration
GCP	Good Clinical Practice
HIPAA	Health Insurance Portability and Accountability Act
ICF	Informed Consent Form
ICH	International Conference on Harmonization
iCRF	Internet Case Report Form
IRB	Institutional Review Board
ITT	Intent to Treat
IV	Intravenous
MCS	Mental Component Score
PC	Personal Computer
PCS	Physical Component Score
PHI	Protected Health Information
PI	Principal Investigator
SAE	Serious Adverse Event
SAS	Statistical Analysis System
SDV	Source Document Verification
SOC	Standard of Care
TEAE	Treatment Emergent Adverse Event
UHMWPE	Ultra High Molecular Weight Polyethylene
UPS	United Parcel Service
USA or U.S.	United States of America
USB	Universal Serial Bus
VAS	Visual Analog Scale
VR-12	Veterans RAND 12 Item Health Survey

6. SYNOPSIS

Study Title	Efficacy of the BioWick® SureLock® Implant for the Reattachment of Soft Tissue to Bone in Subjects Undergoing Rotator Cuff Repairs
Sponsor	Cayenne Medical, Inc., a Zimmer Biomet company
Study Design	The study is a prospective, non-randomized, open-label, single-arm study that includes both preoperative assessments and follow-up assessments at 3 months, 6 months, and 12 months.
Clinical Phase	Postmarket
Number of Sites	Up to ten sites in the U.S.
Study Duration per Subject	Subjects will be enrolled in the study for up to 12 months.
Primary Objective	The primary objective of this study is to assess survivorship (lack of reoperation/device removal) with the use of the BioWick SureLock implant.
Secondary Objective	The secondary objectives of this study are : 
 • To document the postmarket effectiveness of the BioWick SureLock implant using range of motion measurements, ASES scores, VR-12 scores, and VAS scores, with the corresponding assessments made at 3 months, 6 months, and 12 months. • To document device safety via device-related adverse events reported over the course of the study.
Primary Endpoint	The primary endpoint of this study is the BioWick SureLock implant survivorship at 12 months post-operative.
Secondary Endpoints	The secondary endpoints of this study are: 
 • Implant survivorship at visit intervals other than 12 months • VR-12 scores at 3 months, 6 months, and 12 months postoperative • ASES rating scale at 3 months, 6 months, and 12 months postoperative • VAS pain scores at 3 months, 6 months, and 12 months postoperative • Range of motion (ROM) at 3 months, 6 months, and 12 months postoperative

Inclusion Criteria	
Inclusion Criteria
 
 1. Clinical diagnosis of rotator cuff tear which is greater than or equal to 1.5 cm and less than or equal to 4.0 cm full thickness of either the supraspinatus or infraspinatus determined by MRI which has not been previously repaired; 2. Goutallier Stage 2 or less; 3. Patte Stage II (mid humeral head retraction); 4. Tear(s) confirmed intra-operatively by calibrated probe, tears measured in both anterior-posterior and medial-lateral planes; 5. Subject is skeletally mature at the surgical site; 6. Subject is able to read and understand the ICF and has voluntarily provided written informed consent.
Exclusion Criteria	
 1. Clinical diagnosis of a rotator cuff tear of the subscapularis that requires repair (not including debridement); 2. Conditions which, in the opinion of the Principal Investigator, may limit the subject's ability or willingness to follow post-operative care or study instructions; 3. If female, subject is pregnant; 4. Presence of local or systemic infection; 5. Suprascapular nerve compression requiring release or documented by EMG-NCV; 6. Substance abuse, including tobacco, alcohol, or illicit drugs which, in the investigator's judgment, could impair healing or influence study compliance; 7. Foreign body sensitivity. If material sensitivity is suspected, testing should be completed prior to device implantation; 8. Insufficient blood supply or previous infection which may hinder the healing process; 9. Subject conditions including: insufficient quantity or quality of bone or soft tissue, or immature bone where the device may impact or disrupt the growth plate; 10. Subject is a prisoner or member of another vulnerable population; 11. Cortisone injection within 6 weeks prior to surgical treatment; 12. Use of immune suppressants or chemotherapeutic medications within the last 12 months;

	13. Use of systemic corticosteroids at any daily dose for more than 1 month within the last 12 months.
Safety Evaluation	Safety evaluations will be based on the frequency and incidence of device related adverse events.
Planned Sample Size	A maximum of 71 subjects will be enrolled in the study.
Statistical Analysis	
The following analysis populations will be defined for the study:
 
Intention to Treat (ITT) Population – The ITT population will consist of all subjects who have signed informed consent, been enrolled in the study, and have had successful placement of the BioWick™ SureLock™ implant.
 
Safety Population – The safety population will consist of all subjects who have signed informed consent, been enrolled in the study, and have had a procedure during which BioWick SureLock implant placement was attempted, whether or not placement was successful.
 
The primary analysis population for all primary and secondary endpoints will be the ITT population. The primary analysis population for safety will be the safety population.
 
Analysis of Primary Endpoint Implant survivorship for each subject will be determined by whether the subject undergoes a device removal/revision/reoperation of the study device.

7. SCHEDULE OF STUDY EVENTS

Table 7.1 Study Flowchart of Scheduled Events

Event	Screening (Day -28 to -1)	Enrollment/ Visit 1 (Day 1) ¹	3 Months/ Visit 2 (Day 90 ± 14 Days)	6 Months/ Visit 3 (Day 180 ± 30 Days)	12 Months/ Visit 4 Or Early Termination Visit ² (Day 365 ± 30 Days)
Informed Consent	X				
Inclusion/Exclusion Criteria	X	X			
Medical History	X				
Physical Exam	X				
Concomitant Medications	X	X	X	X	X
BioWick SureLock Surgical Implantation		X			
Magnetic Resonance Imaging	X ³				
ASES Rating Scale	X		X	X	X
VR-12 Health Survey	X		X	X	X
ASES Range of Motion	X		X	X	X
Adverse Events	X	X	X	X	X
Subject Completion					X

¹ Upon meeting all I/E criteria, subjects will be enrolled on Day 1 after final confirmation of intra-operative I/E criteria.

² Assessments to be completed if the subject is an early withdrawal and returns to the clinic for a final visit.

³ A MRI scan obtained within 6 months of screening may be used to confirm I/E criteria. If a MRI scan is not available within this time frame, then a screening MRI scan is required.

8. ETHICAL CONSIDERATIONS

This clinical study is designed to comply with International Conference on Harmonization (ICH) Guidance on General Considerations for Clinical Trials (62 FR 66113, 17 Dec 1997), Clinical Investigation of Medical Devices for Human Subjects -- Good Clinical Practice (ISO14155:2011), and Good Clinical Practice: Consolidated Guidance (62 FR 25692, 09 May 1997).

8.1 Institutional Review Board

It is the responsibility of the investigator to obtain the approval of the IRB before the start of the study. The IRB must be registered and active with the Office for Human Research Protections of the US Department of Health and Human Services. A copy of the approval letter along with a roster of IRB members and/or the US Department of Health and Human Services Federal Wide Assurance Number will be retained as part of the study records. During the course of the study, the investigator will provide timely and accurate reports to the IRB on the progress of the study at appropriate intervals (not to exceed 1 year) and at the completion of the study. The investigator will notify the IRB of SAEs, protocol deviations or other significant safety findings per IRB guidelines. The study protocol, ICF, advertisements (if any), and amendments (if any) will be approved by the IRB in conformance with CFR, Title 21, Part 56.

8.2 Ethical Conduct of the Study

The study will be conducted in full compliance with applicable FDA regulations and ICH guidelines for GCP and in accordance with the ethical principles that have their origins in the Declaration of Helsinki.

8.3 Subject Information and Consent

A copy of the proposed informed consent documents will be submitted to the Sponsor for review and approval before submission to the appropriate IRBs. The study will not begin until the documents have been reviewed and approved by the Sponsor and the documents have been approved by the IRBs.

The ICF shall contain all of the elements of informed consent specified in the Code of Federal Regulations (21 CFR 50.25) and HIPAA authorization. Copies of the regulations relating to informed consent and the protection of human subjects in clinical studies are available from the Sponsor.

All potential study subjects will be given copies of the following before participating in any screening procedures:

- The study ICF;
- Agreement for HIPAA Authorization (if separate from ICF);
- Any specific documentation that may be required by the site's IRB.

Subjects will have an opportunity to discuss the contents of these forms with study site staff. The study should be thoroughly explained including the purpose of the study, methods, anticipated benefits, and potential hazards prior to obtaining written consent.

Subjects must understand and voluntarily sign these forms in compliance with 21 CFR, Part 50, before participating in any study-related procedures. Subjects will be made aware that they may withdraw from the study at any time.

The subject will be made aware of his/her right to see and copy his/her records related to the study for as long as the investigator has possession of this information. If the subject withdraws consent and/or HIPAA authorization, the investigator can no longer disclose health information, unless it is needed to preserve the scientific integrity of the study. A copy of the signed informed consent document will be given to the subjects for their records.

The subjects will also be informed that their medical records may be reviewed by the study Sponsor or designee, quality assurance auditor, or inspector from FDA or similar foreign authorities. The subjects will be informed that these persons are bound by the same confidentiality obligations as the subject's physician.

Nothing in these regulations is intended to limit the authority of a physician to provide emergency medical care under applicable regulations. Regulations require that Investigators

permit the Sponsor, Sponsor representatives, and appropriate regulatory agencies to conduct inspections and review records pertaining to clinical investigations.

The delegation of Investigator responsibilities, including obtaining informed consent, must be documented in the study records.

8.4 Subject Confidentiality

The Principal Investigator and designees, employees, and agents involved with this study will comply with relevant state and federal laws relating to the confidentiality, privacy, and security of subject's PHI. They will only create, maintain, use, or disclose any data that is generated by this study or other information disclosed to the Principal Investigator or their employees or agents during the course of the study to the Sponsor, IRB, FDA, or other authorized recipients as appropriate for the execution, analysis, review, and reporting of this study. Such information shall not be used for any other purposes and will remain confidential.

Subject records are only to be identified by initials and subject ID numbers. Subject names are not to be transmitted on any document to the Sponsor.

9. INTRODUCTION

9.1 Background and Current Treatment

Fixation in soft tissues is traditionally achieved by using a solid anchor which has been loaded with non-absorbable sutures, a technique which has proven adequately effective but which carries the risk of displacement or relocation of the anchor as well as bone loss and/or articular damage. Additionally, existing products require manual "tugging" of the anchor in order to achieve deployment, and, in the event that the anchor is not deployed correctly, the anchor may subsequently pull out.

9.2 BioWick SureLock Implant

The BioWick SureLock implant is a device for shoulder and extremity surgery, constructed of Ultra High Molecular Weight Polyethylene Suture. BioWick SureLock is uniquely designed to minimize these risks by avoiding manual tensioning with an inserter mechanism that ensures that the implant is consistently deployed below the cortex.

9.3 Rationale for This Study

The purpose of this study is to collect postmarket data in subjects who receive surgical treatment of a full-thickness rotator cuff tear (of at least 1.5 cm) with the BioWick SureLock implant. Both performance and safety data will be collected.

10. OBJECTIVES

10.1 Primary Objective

The primary objective of this study is to assess survivorship (lack of reoperation/device removal) with the use of the BioWick SureLock implant.

10.2 Secondary Objectives

The secondary objectives of this study are:

- To document the postmarket effectiveness of the BioWick SureLock implant using ASES scores, VR-12 scores, and VAS scores, with the corresponding assessments made at 3 months, 6 months, and 12 months postoperative.
- To document the postmarket effectiveness of the BioWick SureLock implant using range of motion (ROM) measurements with the corresponding assessments made at 3 months and 6 months postoperative.
- To document device safety via device-related adverse events reported over the course of the study.

11. STUDY DESIGN

The study is a prospective, non-randomized, open-label, single-arm, postmarket, multicenter study. The schedule of study events list the procedures to be performed in each visit (see Table 7.1).

11.1 Measures Taken to Avoid Bias

11.1.1 Randomization

All subjects enrolled in the study will be treated with the BioWick SureLock implant. As there is no comparison arm, there will be no randomization.

11.1.2 Blinding

As this study is a single-arm study in which all subjects are treated with the BioWick SureLock implant, neither subjects nor investigators will be blinded.

11.1.3 Description of the Study Device

The BioWick SureLock implant is a device constructed of ultra-high molecular weight polyethylene suture for use in shoulder and extremity surgery. The BioWick SureLock implant eliminates manual tensioning through a unique inserter-controlled deployment method that prevents partial deployment as well as displacement or partial deployment of the anchor by consistent deployment of the anchor below the cortex. The inserter is made of surgical grade stainless steel and plastic, and the wick component is made of 85/15 PLGA (L-lactide-cogluconide).

12. SELECTION OF STUDY POPULATION

Subjects will be recruited from patients requiring rotator cuff repair surgery or have previously had a rotator cuff tear repaired using the BioWick SureLock implant.

12.1 Inclusion Criteria

Subjects must meet all of the following inclusion criteria to participate in this study:

Inclusion Criteria

1. Clinical diagnosis of rotator cuff tear which is greater than or equal to 1.5 cm and less than or equal to 4.0 cm full thickness of either the supraspinatus or infraspinatus determined by MRI, which has not been previously repaired;
2. Goutallier Stage 2 or less;
3. Patte Stage II (mid humeral head retraction);
4. Tear(s) confirmed intra-operatively by calibrated probe, tears measured in both anterior-posterior and medial-lateral planes;
5. Subject is skeletally mature at the surgical site;
6. Subject is able to read and understand the ICF and has voluntarily provided written informed consent.

12.2 Exclusion Criteria

Any subject who meets any of the exclusion criteria will be excluded from participation in this study:

1. Clinical diagnosis of a rotator cuff tear of the subscapularis that requires repair (not including debridement);
2. Conditions which, in the opinion of the Principal Investigator, may limit the subject's ability or willingness to follow post-operative care or study instructions;
3. If female, subject is pregnant;
4. Presence of local or systemic infection;
5. Suprascapular nerve compression requiring release or documented by EMG-NCV;
6. Substance abuse, including tobacco, alcohol, or illicit drugs which, in the investigator's judgment, could impair healing or influence study compliance;
7. Foreign body sensitivity. If material sensitivity is suspected, testing should be completed prior to device implantation;
8. Insufficient blood supply or previous infection which may hinder the healing process;
9. Subject conditions including: insufficient quantity or quality of bone or soft tissue, or immature bone where the device may impact or disrupt the growth plate;
10. Subject is a prisoner or member of another vulnerable population;
11. Cortisone injection within 6 weeks prior to surgical treatment;
12. Use of immune suppressants or chemotherapeutic medications within the last 12 months;

13. Use of systemic corticosteroids at any daily dose for more than 1 month within the last twelve months.

12.3 Subject Withdrawal

Subjects may discontinue from the study at any time. A subject may be discontinued from the study for the following medical or administrative reasons:

- **Subject Withdrawal of Consent** - Subjects will be free to discontinue from the study at any time and for any reason but must notify the study site of their exit from the study.
- **Adverse Event** – If during the procedures the subject suffers an AE that, in the judgment of the PI, Sponsor or medical monitor, presents an unacceptable consequence or risk to the subject, the subject will be discontinued from further participation in the study.
- **Lost to Follow Up** – Subjects discontinue from the study without notifying the study site.
- **Serious Protocol Violation** – If, during enrollment in the study, the subject fails to follow, violates or refuses to participate in any of the procedures described in the protocol then the subject will be discontinued from the study at the discretion of the Sponsor. If, at any point during the study, a subject is determined to have been erroneously enrolled into the study, the subject will be discontinued from the study due to protocol violation.
- **Other** - If the above reasons are not applicable, “Other” will be selected as the option and the appropriate reason for subject withdrawal provided.

For subjects who discontinue or are withdrawn from the study for any reason, the PI will notify the Sponsor and attempt to recover the following:

- AE occurrences since the last visit to the study site
- Concomitant medication usage since the last visit to the study site

If the subject is withdrawn at a study visit, the procedures for an early termination visit will be conducted to assess their continued well-being.

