13.5.6 Coronavirus (COVID-19) Expectations

If subjects are not allowed at the clinic for visits or if subjects refuse to come into the clinic due to COVID-19, then the following tasks should take place:

- Subject questionnaires (VAS, ASES, and VR-12) will be mailed to the subject for completion. These questionnaires should not be completed via phone. If the site does not receive a response from the subject, the site must attempt to contact the subject

and/or re-mail the subject questionnaires at least three (3) times within the visit window before submitting a protocol deviation, unless a response is received.

- The site will attempt to contact the subject to inquire of adverse events that may have occurred and/or been resolved since their last visit. The site is required to perform at least three (3) contact attempts to obtain this information. These contact attempts must be documented in the subject's study binder. If there is no response by the end of the visit window, a note-to-file (NTF) must be added to the subject's study binder indicating new adverse events were not confirmed for the visit.
- ROM measurements will not be required; however, a protocol deviation must be submitted.
- Label protocol deviations as being related to COVID-19, as applicable

Please note that these expectations are *specifically* for COVID-19 situations. If a subject misses a visit unrelated to COVID-19, this section does not apply and a "Missed Visit" protocol deviation will be submitted.

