16.5 Statistical and Analytical Plans

16.5.1 Primary Endpoint Analyses

Implant survivorship for each subject will be determined by whether the subject undergoes a revision or reoperation of the study device. Survivorship will be assessed using a Kaplan-

Meier analysis. Data will be considered right-censored for all patients that do not have a device failure. For patients lost-to-follow-up, their last available clinical visit will be used as the censored date. For patients that die during the study, their death date will be used as the censored date. The survivorship point estimate and 95% confidence interval about the point estimate will be calculated for the one-year primary endpoint.

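### Reoperation status is not ascertained after withdrawal and the analysis of withdrawn subjects is undefined, so one-year survivorship may be overestimated if withdrawal is related to later device failure

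*Combined protocol and SAP*

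**What the plan says.** The primary endpoint is freedom from reoperation or device removal at 12 months (15.1.1), estimated by Kaplan-Meier (16.5.1). Enrolment takes place intra-operatively (13.2), and the ITT population is the enrolled subjects with successful placement (16.3). A subject withdrawn after surgery is therefore normally an implanted member of the primary analysis population.

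Section 12.3 gives three routes by which the sponsor or investigator can end participation:

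- **Adverse event.** For an AE suffered in the course of the procedures and judged to present unacceptable risk, "the subject will be discontinued from further participation in the study".
- **Non-compliance.** If the subject does not follow the protocol, "then the subject will be discontinued from the study at the discretion of the Sponsor".
- **Erroneous enrolment.** If this comes to light at any time, "the subject will be discontinued from the study due to protocol violation".

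For every withdrawal the site tries to recover two items: "AE occurrences since the last visit to the study site" and "Concomitant medication usage since the last visit to the study site". Early-termination procedures apply only when the withdrawal happens at a study visit. Under 17.4, AEs are recorded from consent until the subject terminates from the study.

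On the analysis side, 16.5.1 right-censors everyone without a device failure. It gives a date for deaths and, for patients lost to follow-up, says that "their last available clinical visit will be used as the censored date". It gives no date for the withdrawals above. Section 16.6 restricts the primary analysis to subjects with an evaluable endpoint, as a complete-case analysis.

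**The concern.** Kaplan-Meier treats a censored subject as having the same future risk as those still under observation. If subjects leave for reasons connected with how the repair is doing, and no one learns whether they were later reoperated, failures go uncounted and survivorship looks better than it is.

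The link is plausible for a subject withdrawn because of an unacceptable AE. It is also conceivable for erroneous enrolment, because several exclusions in 12.2 concern healing (blood supply, quality of bone or soft tissue, systemic corticosteroids). For non-compliance there is no evident direction.

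A second problem is separate from bias. Two analysts following the plan could handle the same withdrawn subject differently: one would censor on a date of the analyst's choosing (16.5.1), the other would drop the subject (16.6).

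**Working it through.** **Tracing a withdrawn, implanted, event-free subject through the plan**

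1. Before exit: AEs since the last visit are sought (12.3), so a reoperation that has already happened has a route into the data, although it is not a named item.
2. From exit to Day 365: AE recording has stopped (17.4). "Table 7.1 Study Flowchart of Scheduled Events" schedules nothing after the early-termination visit. No section asks for device status.
3. At analysis: 16.5.1 censors without a stated date and 16.6 drops. The two rules conflict.

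**Size**

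The plan gives no number of withdrawals and no failure risk for them, so there is no plan figure to reproduce on this point. Inputs from 16.2: one-year survivorship 85%, total 71, loss 15%. Assumptions: *m* subjects withdrawn, and *k*, the ratio of 12-month failure risk in withdrawn to retained subjects.

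*Per missed failure.* 1/71 = 1.4 points. Expected failures: 0.15 × 71 = 10.65.

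*All withdrawals early, none of their failures seen.* If overall failure is 15%, the risk among retained subjects is f = 10.65 / [(71 − m) + m·k]. Kaplan-Meier tends to 1 − f, so the bias is 15% − f. I take m = 4 as an illustration and m = 11 because 15% of 71 is 10.65.

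| m | k | f | Bias (points) |
|---|---|---|---|
| 4 | 0.5 | 10.65/69 = 15.4% | −0.4 |
| 4 | 1 | 10.65/71 = 15.0% | 0 |
| 4 | 2 | 10.65/75 = 14.2% | +0.8 |
| 4 | 3 | 10.65/79 = 13.5% | +1.5 |
| 11 | 0.5 | 10.65/65.5 = 16.3% | −1.3 |
| 11 | 1 | 10.65/71 = 15.0% | 0 |
| 11 | 2 | 10.65/82 = 13.0% | +2.0 |
| 11 | 3 | 10.65/93 = 11.452% | +3.5 (3.548) |

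*Withdrawals spread evenly over the year.* In a large simulation the hazard was constant, giving 85% in retained subjects, and was multiplied by k after withdrawal. Bias in points under each rule:

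| Withdrawn | k | Kaplan-Meier (16.5.1) | Complete case (16.6) |
|---|---|---|---|
| 4/71 | 1 | 0 | −0.4 |
| 4/71 | 2 | +0.4 | 0 |
| 4/71 | 3 | +0.7 | +0.3 |
| 11/71 | 1 | 0 | −1.2 |
| 11/71 | 2 | +1.0 | −0.2 |
| 11/71 | 3 | +1.9 | +0.75 |

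The sign therefore depends on k and on which of the two conflicting rules is applied.

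*Bounds without any assumption on k.* If 85% of retained subjects survive, full ascertainment would give between 0.85 × 67/71 = 80.2% and (0.85 × 67 + 4)/71 = 85.8% for m = 4. For m = 11 the range is 0.85 × 60/71 = 71.8% to (0.85 × 60 + 11)/71 = 87.3%.

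*Yardstick.* Section 16.2 states a 95% half-width of 10.7 points. The Wald value at its 59 subjects is 1.96 × √(0.85 × 0.15/59) = 9.1 points. That mismatch is a separate matter; either way the modelled biases are well inside the sampling error.

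**The case against.** Several arguments against the point have force.

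- **The AE route may be narrow.** Its trigger is an AE arising in the course of the procedures, under a lead-in that is permissive. After surgery, participation consists of questionnaires, range of motion, and AE and medication questions, so few later AEs may lead to withdrawal. This stands and limits the likely number, but the other two routes remain, and the erroneous-enrolment one is mandatory.
- **Reoperation before exit can be captured.** AE recovery is attempted for every withdrawal, AE records carry dates, action taken and outcome (17.4), and SAE follow-up is supplied on request (17.3). The CRFs are not among the documents, so the lack of a row in Table 7.1 does not show that no date is collected. This stands: the gap lies after withdrawal, not before it.
- **The last-clinical-visit rule is a side issue.** It applies only to patients lost to follow-up. It can discard event-free time confirmed remotely, since under 13.5.6 "The site will attempt to contact the subject to inquire of adverse events", but it does not govern AE or violation withdrawals.
- **The stakes are moderate.** This is a single-arm estimation study with no performance threshold.

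A reader might infer two stronger things: that the estimate is biased upward, and that its confidence interval under-covers. The documents support neither. Upward bias needs k above 1, and the complete-case rule can push the other way: with 15% non-informative loss spread over the year it gives about 83.9% against a true 85%. As to coverage, simulations with n = 71, true survivorship 85%, 15% other loss, and 0, 10, 20 or 33% of failures censored 30 days before reoperation give mean Kaplan-Meier estimates of 85.0, 86.3, 87.6 and 89.6%. A plain Greenwood interval then covers 92, 90, 83 and 70%, but a log-log interval covers 96, 97, 96 and 91%. The plan does not say which interval it will use, and the lost share and the 30-day gap are assumptions.

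**Conclusion.** The point holds as a gap in ascertainment and an undefined analysis rule. As written, the plan can lose primary-endpoint events in implanted subjects between withdrawal and Day 365, and it does not settle whether those subjects are censored, and when, or dropped. One-year survivorship may be overestimated if withdrawal is related to later failure.

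The size is unknown because the documents give neither the number of withdrawals nor their risk. The ranges of +0.8 to +1.5 points (4 withdrawals) and +2.0 to +3.5 points (11) rest on risk ratios of 2 to 3 and on early exit. They are roughly halved if exits are spread over the year, zero at equal risk, and negative at lower risk. This is a cheap improvement worth making, not a demonstrated bias.

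**What to change.** (a) In 12.3 and 17.4, state that withdrawal initiated by the sponsor or investigator ends study procedures but not ascertainment of reoperation or removal. The site obtains that status by contact or record review through Day 365 unless consent is withdrawn. This leaves the grounds for withdrawal untouched.

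(b) Record reoperation or removal of the study device (yes/no, date) at each visit in Table 7.1 and among the items recovered at withdrawal.

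(c) In 16.5.1, censor both lost-to-follow-up and withdrawn subjects at the last date on which device status is known, including by remote contact. Remove the complete-case rule in 16.6 for the Kaplan-Meier primary analysis.

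Cost: amended wording in these sections, one CRF item, and a call or chart check for a few subjects. If the consent form does not already cover contact and record review after study procedures end, it needs a sentence and IRB approval. No added patients or visits.
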